STUDY OBJECTIVES AND HYPOTHESES

Primary objective: To evaluate the efficacy of reduced form CoQ10 (ubiquinol) supplementation in severely burned adult patients in the mitigation of MODS between 72 hours after burn injury and 12 weeks, death, or discharge (whichever comes first).

Primary objective hypothesis: Reduced form CoQ10 supplementation will result in a statistically significant reduction in the incidence of MODS between 72 hours after burn injury and 12 weeks, death, or discharge (whichever comes first) as compared to placebo.

Secondary objectives: To evaluate the effect of reduced form CoQ10 (ubiquinol) supplementation in severely burned adult patients on the following clinical outcome events and biochemical measurements in plasma and urine between 72 hours after burn injury and 12 weeks, death, or discharge (whichever occurs first):

1. The six individual organ systems comprising the MODS score and their times of occurrences,
2. The weighted composite score of the six constituents
3. The maximum total Sequential Organ Failure Assessment (SOFA) score
4. The maximum SOFA score for each organ
5. AUC of total SOFA score (score x days)
6. AUC of SOFA score for each organ (score x days)
7. Delirium (CAM-ICU) (number of days)
8. Length of hospital stay (number of days)
9. Sepsis (Sepsis-3) (number of incidence)
10. Septic Shock (Sepsis-3) (number of incidence)
11. Plasma mitochondrial DNA (4 blood collections)
12. 3-Methylhistidine (3-MH) and creatinine in urine (a biomarker of muscle wasting)

Secondary objective hypothesis: Reduced form CoQ10 supplementation will result in a statistically significant reduction in each of the secondary endpoints between 72 hours after burn injury and 12 weeks, death, or discharge (whichever comes first) as compared to placebo.

RESEARCH DESIGN

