3-Methylhistidine concentrations will be quantified by negative chemical ionization gas chromatography mass spectrometry as described in our previous studies^{52,53}. Urinary creatinine concentrations will be measured by a commercial kit. The average of three measurements on the three consecutive days at each time point will be used for statistical analysis to minimize possible day-to-day variations.

STATISTICAL ENDPOINTS AND APPROACH TO DATA ANALYSIS

This two-arm balanced double blind parallel Randomized Clinical Trial (RCT) study will be performed using an intention to treat (ITT) analysis population that includes all randomized patients.

Primary endpoint: The primary endpoint will be the count of the following events. This count will be used to create a composite score ranging from 0 to 6 by assigning 1 to each event regardless of stage, scores and severity that individual subjects encounter from 72 hours after burn injury through 12 weeks or until death or discharge, whichever occurs first:

1. Acute Kidney Injury (AKI) (KDIGO Stages 1 – 3)
2. ARDS (The Berlin ARDS Definition: Mild, Moderate, Severe)
3. Cardiovascular Dysfunction (SOFA Scores 1 – 4)
4. Coagulopathy (SOFA Scores 1 – 4)
5. Liver dysfunction (SOFA Scores 1 – 4)
6. Death (all causes)

We will calculate mean values of the composite sum scores among the study patients in the CoQ10 and placebo arms, and then test their difference by using an independent samples *t*-test if the observed data are evident to follow a normal distribution by Shapiro-Wilk's test. Otherwise, Mann-Whitney U test will be applied and the group specific medians and quartiles will be used as the summary statistics.

AKI: AKI represents the acute loss of kidney function and is associated with a profound and severe increase in morbidity and mortality in burn patients⁵⁴. Early AKI, which occurs less than 3 days post-burn, is usually related to inadequate fluid replacement during the initial resuscitation. AKI can occur later in the hospitalization and late AKI is multifactorial in origin and often associated with sepsis development⁵⁵. For the purposes of this study, we will follow the definitions and classification guidelines set forth in "AKI of Kidney Disease: Improving Global Outcomes (KDIGO)"^{56,57} (**Table 3**). Published in 2012, this guideline has been used in critically ill patients and in combat-injured populations⁵⁸.

Stage	Table 3. AKI (KDIGO)

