Scientific rationale for the observation period: Studies in trauma patients have suggested the organ dysfunction that develops soon after trauma (i.e., during the first 48 -72 h) rapidly resolves in a high proportion of patients and may reflect the reversible derangement of organ function induced by the inciting event or incomplete resuscitation. Thus, it has been proposed that later assessment of organ function (i.e., 3 days after injury) will yield a more accurate definition of multiple organ failure in trauma patients, which is needed to evaluate the relationship between trauma-induced organ dysfunction and prognosis^{71,72}. In the acute phase, particularly the first 72 hours after severe burn injury, organ dysfunction frequently occurs, causing AKI (e.g., oliguria), cardiovascular dysfunction (e.g., hypotension), and coagulopathy (e.g., thrombocytopenia)⁷³. In some cases, the organ dysfunction is transient and the patient may recover during the late-acute or sub-acute phase. In such cases, the recovery from organ dysfunction is associated with relatively good prognosis. In contrast, if the organ dysfunction continues beyond the acute phase or if it occurs or recurs at a later time, the clinical outcome is typically worse. Therefore, we will evaluate the effects of

CoQ10 supplementation on the aforementioned multi-organ dysfunction that patients encounter beginning 72 hours post-burn injury and thereafter.

Secondary endpoints: Secondary endpoints will be the following outcome events observed from 72 hours after burn injury through 12 weeks or until death or discharge (whichever occurs first) and the biochemical measurements in plasma and urine.

1. The six individual binary outcome MODS events and their times of occurrences, (i.e., the constituents of the primary composite score)
2. Weighted composite score of the six constituents
3. Maximum total SOFA score
4. Maximum SOFA score for each organ
5. AUC of total SOFA score (score x days)
6. AUC of SOFA score for each organ (score x days)
7. Delirium (CAM-ICU) (number of days)
8. Length of hospital stay (number of days)
9. Sepsis (Sepsis-3) (number of incidence)
10. Septic Shock (Sepsis-3) (number of incidence)
11. Plasma mitochondrial DNA (4 blood collections)
12. 3-Methylhistidine (3-MH) and creatinine in urine (a biomarker of muscle wasting)

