Data Analysis: For between-arm comparisons of single valued (either measured at once or as an aggregated variable such as AUC over a period) outcomes, we will apply chi-square test if the outcome is binary, and *t*-test or Mann-Whitney *U*-test to continuous outcomes based on the best fit of Shapiro-Wilk's test. The between-arm difference in the distributions of times to the first event and multiple events (of the six constituents) will be examined by using single event time Cox's model and the times to correlated multiple events using Cox's model allowing multivariate frailty, respectively. The incidence rates of each individual event, with- and without differentiating its severity, as a binary outcome will be compared between the two arms by means of longitudinal logistic modeling with generalized estimating equation (GEE)⁸⁴ to allow more than one events per patient. For the repeated measures analysis of the longitudinal plasma mitochondrial DNA and urine 3- methylhistidine (3-MH), we will examine if the mean levels over time are different between the two arms by using longitudinal general linear mixed effects model⁸⁵ which will provide the within group time dependency patterns as a linear effect or more complex form of non-linear patterns which would be able to characterize the time dependent treatment effects over time along with testing for time \times group interaction(s) of those model parameter(s). Total and organ-specific SOFA scores over time will also be examined by this mixed effects models of which the

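### Length of stay stops at death and raw days are compared, so an early death counts as a short, favourable stay; delirium days and SOFA AUC also lack a stated rule for death

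*Combined protocol and SAP*

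**What the plan says.** All references are to the combined protocol and SAP.

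- **Secondary endpoints:** outcomes are "observed from 72 hours after burn injury through 12 weeks or until death or discharge (whichever occurs first". Items 5, 7 and 8 are "AUC of total SOFA score (score x days", "Delirium (CAM-ICU) (number of days" and "Length of hospital stay (number of days". Item 6 is the same AUC for each organ.
- **Secondary objective hypothesis:** "Reduced form CoQ10 supplementation will result in a statistically significant reduction in each of the secondary endpoints".
- **Statistical Endpoints and Approach to Data Analysis:** the trial uses "an intention to treat (ITT) analysis population that includes all randomized patients", so patients who die are included.
- **Data Analysis, single-valued outcomes:** "For between-arm comparisons of single valued (either measured at once or as an aggregated variable such as AUC over a period) outcomes", the plan uses a chi-square test if the outcome is binary and a t-test or Mann-Whitney test if it is continuous, chosen by Shapiro-Wilk.
- **Data Analysis, event times:** "The between-arm difference in the distributions of times to the first event and multiple events (of the six constituents) will be examined" with Cox models. Length of stay is not one of those six events.
- **Rationale for the clinical secondary endpoints:** for SOFA AUC the plan points to a published method without restating it.
- **Missing data:** the text covers withdrawal, missing at random and multiple imputation if needed. It does not mention death.

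**The concern.** Each of the three totals can stop growing for two opposite reasons: the patient went home or the patient died. The planned comparison does not distinguish them, and a smaller total is the hypothesised benefit.

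The problem is clearest for length of stay. The inclusion criteria require an expected stay of at least two weeks, so a death before day 14 is recorded as a shorter stay than was anticipated for anyone enrolled. A death late in the 12 weeks is recorded as a long stay. A mortality difference therefore moves the comparison in a direction set by when deaths occur, not by recovery.

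For delirium days and SOFA AUC, the effect also depends on how the patient scored before death. At stake is a secondary result that could mislead when read on its own.

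**Working it through.** **Inputs from the plan.** Table 6 assumes death in 8% on placebo and 6.4% on CoQ10 (0.08 × 0.8 = 0.064). With 290/2 = 145 per arm, that is 145 × 0.08 = 11.6 and 145 × 0.064 = 9.3 expected deaths. Pilot Table 1 gives mean stays of 22.0 and 21.9 days, but mean burn size there was 19.4% and 13.9% TBSA, against 20–70% here. The plan states no expected stay, delirium or AUC figure, so there is none to reproduce.

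**Assumptions (not in the documents).** Survivor stays of 30–45 days, the timing of deaths, the 16% and 12% CoQ10 death rates, and the SOFA and delirium levels before death.

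**Step 1: shift in mean stay at the plan's death rates.** If survivors' stay is the same in both arms, the difference (CoQ10 minus placebo) is (0.064 − 0.08) × (day of death − mean survivor stay).

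- Early deaths: −0.016 × (14 − 30) = +0.26 days; −0.016 × (10 − 45) = +0.56 days.
- Early deaths, 22-day stay: −0.016 × (14 − 22) = +0.13; −0.016 × (10 − 22) = +0.19.
- Death on day 60: −0.016 × (60 − 45) = −0.24; −0.016 × (60 − 30) = −0.48; −0.016 × (60 − 22) = −0.61.

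A positive value counts against CoQ10. So better survival is slightly penalised if deaths are early and slightly rewarded if they are late.

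**Step 2: an assumed harm case.** This was simulated with 145 per arm, two-sided 5%, and 2,000 to 4,000 trials per setting. Survivor stay was lognormal (log-SD 0.5, limited to 5–84 days) and identical in both arms. Deaths were uniform over the stated days. The table gives the share of trials in which the raw Mann-Whitney test significantly favours CoQ10 (nominal 2.5%).

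| Survivor stay | Deaths on days | 16% v 8% | 12% v 8% |
|---|---|---|---|
| median 35 | 4–20 | about 19% | about 8% |
| median 35 | 4–42 | about 9% | 4.7% |
| median 35 | 30–80 | 0.4–0.5% | 1.2% |
| mean 22 | 4–20 | 10–11% | 5.4% |
| mean 22 | 4–42 | about 2% | 2.3% |
| mean 22 | 30–80 | 0.1–0.2% | 0.6% |

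**Step 3: would the deaths reveal it?** At 16% v 8%, only about 0–3% of trials show the false benefit without a significant chi-square excess of CoQ10 deaths. At 12% v 8% the figure reaches about 4%.

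**Step 4: the alternative.** The test used was a log-rank test on time to live discharge, with deaths kept at risk to day 84. In the same excess-mortality settings it gives false benefit in at most 0.4% of trials. It shows fewer live discharges on CoQ10 in about 33–42% of trials at 16% v 8% and 12–16% at 12% v 8%.

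**Step 5: the other two endpoints.**

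- *SOFA AUC.* A death on day 10, counted from 72 hours, accrues 7 × 8 = 56 to 7 × 12 = 84 score-days at an assumed daily SOFA of 8–12. A patient discharged on day 22 (19 days) exceeds that only with an average SOFA above 56/19 = 2.9 to 84/19 = 4.4. Either patient can have the larger AUC.
- *Delirium days.* The settings were 16% v 8%, deaths on days 4–20 or 4–42, and survivors delirious on 20% of days. False benefit is 11–14% if patients who die are almost never scored positive. It is 2.7–5.9% if they are positive on 20% of days and 0.5–2.2% if on 60%. This is illustrative only.

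**The case against.** The strongest reply is that the worrying case is assumed and the plan's other outputs would expose it. The sponsor expects fewer deaths on CoQ10, and at those rates the shift is under 1 day and, with early deaths, conservative. Death is a component of the primary score and is also reported as an individual event with its time. This largely stands: Step 3 shows that a false length-of-stay benefit would usually arrive with a visible excess of deaths. It limits the severity, but it does not make the length-of-stay p-value interpretable.

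A second reply is that the alternative is itself driven by mortality. That is true. With plan rates and no effect on survivors' stay, the competing-event test favours CoQ10 in about 5–6% of trials (nominal 2.5%), while the raw test goes against CoQ10 in 4.4% (35-day median, deaths on days 4–20). The difference is that the competing-event result moves in a direction consistent with survival.

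Multiple imputation is no answer, because a stay ended by death is an observed value and not a missing one.

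Some stronger readings are tempting but not supported:

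- *SOFA AUC has no rule for death at all.* The cited source may contain one; the plan simply does not state it.
- *The error favours CoQ10.* No direction is fixed.
- *The SOFA mixed model should be described as conditional on being alive and in hospital.* A likelihood-based mixed model under missing at random does not estimate that. It implicitly extrapolates scores past death and discharge, so such a sentence would be wrong.

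**Conclusion.** The point holds for length of stay as a stated rule that can mislead, and for delirium days and SOFA AUC as a handling of death that the plan does not state. At the plan's own mortality the effect is small: about 0.1–0.6 days against CoQ10 with early deaths, and reversed with late ones. In the assumed 16% v 8% case, false benefit runs from about 19% of trials (35-day median stay, deaths on days 4–20) to under 1% (deaths on days 30–80). It is about 0–3% once trials with a significant excess of deaths are set aside. These percentages rest on assumed stays, death windows and mortality.

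A reader might infer that the trial could declare success while hiding harm. The documents do not support that: only secondary endpoints are affected, and death is in the primary endpoint and reported separately. The risk is a misleading length-of-stay result read alone. This is a cheap improvement of low severity.

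**What to change.** 1. **Length of stay.** In Data Analysis, replace the test on raw days with time to live discharge through 12 weeks, with death as a competing event. Show cumulative incidence of live discharge by arm, compared by Gray's test. Censor patients still in hospital at 12 weeks, and withdrawals at the date of withdrawal. Report raw days descriptively. Amend item 8 of the secondary endpoints and the secondary hypothesis to say that benefit means earlier live discharge.
2. **Delirium days and SOFA AUC.** Keep the planned raw comparison as the main analysis. Add a Mann-Whitney test with deaths ranked worst as a prespecified sensitivity analysis. State that no reduction is claimed if the worst-rank result points the other way. Write the AUC's handling of death into the plan rather than leaving it to the cited source.
3. **All three.** Report mortality by arm and survivor-only descriptives beside each result.

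**Cost.** A few sentences in the hypothesis, endpoint, rationale and analysis sections, and modest programming with dates and scores already collected. The length-of-stay estimand does change, and the amendment should say so. The downside is that a mortality difference alone can move the competing-event and worst-rank results, which is why item 3 is part of the fix.

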Brief study overview: We will conduct a two-arm, prospective, double-blind, randomized, placebo-controlled clinical trial to evaluate the efficacy and safety of reduced form CoQ10 (ubiquinol) supplementation in severely burned adult patients (total n=290) at 15 mature burn centers across North America. Stratified block randomization will take place by site and Revised Baux score. The formula for the Revised Baux score is: Age + Percent Burn (%TBSA) + 17 x (Inhalation Injury, 1 = yes, 0 = no). This formula has been widely adopted for mortality prediction in burn patients^{45,46}. In previous studies, a trend has been shown for a sharp increase in mortality when the Revised Baux score exceeds approximately 110^{45,47,48}. Therefore, patients enrolled in this study will be stratified for randomization into two groups based on the Revised Baux score: (1) less than 110; and (2) equal to or greater than 110. The intervention will consist of a loading dose of reduced form CoQ10 of 1,800 mg/day tid for 4 weeks to be followed by a maintenance dose of 600 mg/day once daily from weeks 5 to 12. The intervention or allocation-controlled placebo will be administered by 72 hours after injury and will continue until 12 weeks after injury or until death or discharge, whichever comes first. Oral tablets (600 mg/tablet) will be administered to CoQ10 subjects who can swallow while a liquid form (100 mg/mL) will be administered to CoQ10 subjects requiring an enteral tube for nutrition. There will be no post-discharge study procedures.

Study investigators, personnel, and centers:

[name] MD, MSCS; UT Southwestern Medical Center/Parkland Memorial Hospital
[name]; Wake Forest University School of Medicine
[name]; University of Texas Medical Branch- Galveston
[name]; The Ohio State University Wexner Medical Center
[name]; University of Alabama-Birmingham Medical Center
[name]; University of Kansas Medical Center
[name]; University of Michigan
[name]; Case Western Reserve University School of Medicine
[name]; Massachusetts General Hospital
[name]; Loyola University Medical Center
[name]; Temple University
[name]; Columbia St. Mary's-Wisconsin
[name]; University of California- Davis
[name]; University of South Florida
[name], MD; University of South Florida
[name]; Hennepin County Medical center

[name], CRA; American Burn Association

[name], MSN; UC Davis, American Burn Association

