particular interest is to test if the improvement in the longitudinal mean SOFA scores is greater during certain time window. All analyses will also be extended to adjust for the influencing effects of any baseline demographic and/or clinical indications. Missing data may be unavoidable. Because the informed consent from many study enrollees will be obtained through the family members (i.e., surrogates), a small portion (up to 2% attrition rate) of the enrolled patients may voluntarily withdraw from the study. Before final analysis, we will check the missing data pattern of the outcomes first. If there are systematic differences in missing data patterns between the study groups and/or patient characteristics (e.g., burn type), we will take into account such problems in the analysis. The longitudinal mixed effects modeling will provide unbiased and consistent estimates of the effects provided that the missing data mechanism is ‘missing at random’ (MAR). If necessary, multiple-imputation will be applied to all endpoints analyses. All statistical tests will be two-sided and will adopt a 5% significance level.

Sample size calculation: The sample size of 290 study patients for this study is determined to achieve an adequate statistical power at a 5% Type-1 error rate for the primary endpoint analysis by the following statistical calculations. We first estimated the expected means and variances of the composite scores (assuming the six individual events are independent) for the Control and CoQ10 treatment arms under the assumption depicted in **Table 6** via 1000 repeated simulated data sets ($n = 5000$ each), instead of calculating them algebraically.

Each simulation run calculated the means and variances of the two arms, and the resulting average means (and variances) over 1000 simulations were 2.43 (1.04) in the placebo arm and 1.94 (1.05) in CoQ10 arm respectively. Based on the assumption about the event incidence rates and the estimated means and variances of the composite scores from the simulated data sets, the calculated required sample size per treatment arm (using PASS¹¹⁰) to detect such a difference (i.e., 20% reduction in the overall events) with 80% power at a 5% Type-1 error rate using 2-sided independent samples t-test was 142 per arm.

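### The GEE comparison of organ-event incidence has no stated row unit or post-discharge status; if rows are hospital days or weeks, a shorter stay on CoQ10 can dilute or reverse a real benefit

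*Combined protocol and SAP*

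**What the plan says.** The Data Analysis section compares the incidence of each individual event, with and without regard to severity, "by means of longitudinal logistic modeling with generalized estimating equation (GEE". The reason given is "to allow more than one events per patient". It does not say whether a row is a day, a week, an episode or an event type, and it names no weights and no working correlation.

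The same section has a general rule for outcomes with a single value per patient: "we will apply chi-square test if the outcome is binary". It also plans Cox models for first and multiple events. No order of importance is given among these analyses.

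Under Secondary endpoints, the events are those "observed from 72 hours after burn injury through 12 weeks or until death or discharge (whichever occurs first"; the Primary endpoint paragraph uses the same window. The Brief study overview adds: "There will be no post-discharge study procedures".

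On missing data, the section says: "The longitudinal mixed effects modeling will provide unbiased and consistent estimates of the effects provided that the missing data mechanism is" MAR. It expects up to 2% voluntary withdrawal and adds: "If necessary, multiple-imputation will be applied to all endpoints analyses". Discharge is not described as missing data.

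The Secondary objective hypothesis expects a reduction in every secondary endpoint on CoQ10. Length of hospital stay is number 8 on that list.

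**The concern.** A longitudinal model that allows several events per patient is most naturally read as having repeated rows over the hospital stay. A patient who recovers and goes home stops supplying event-free rows, while a patient who stays ill keeps supplying rows. The number of rows is then itself a result of treatment, and the odds ratio describes periods in hospital.

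The distortion arises when the arms differ in length of stay, which is what the protocol hopes to show. Event-days and hospital days would then fall together and their ratio would move towards 1. If stay falls proportionally more than event-days, the ratio passes 1. A null or adverse-looking odds ratio for kidney, lung, cardiovascular, coagulation or liver events could stand beside fewer affected patients, and the report would have no rule for reconciling the two.

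Unweighted GEE is in general valid only when missingness is completely at random or depends only on covariates in the model. Discharge depends on recovered organ function. The MAR sentence is about the mixed models.

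**Working it through.** The documents give no figure for the GEE comparison, so there is none to reproduce. The check asks when the in-hospital odds ratio departs from a per-patient comparison.

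**1. Closed form.** With treatment as the only covariate and an independence working correlation, the GEE estimate on daily rows is the odds ratio of p = D/L. Here D is mean event-days and L is mean hospital days after hour 72. The window is 84 − 3 = 81 days.

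Assume control D = 5 and L = 25, and that CoQ10 cuts D by 20% to 4. The control odds are 5/20 = 0.250.
- Stay unchanged: 4/21 = 0.190, OR 0.76.
- Stay 10% shorter (22.5): 4/18.5 = 0.216, OR 0.86.
- Stay 20% shorter (20): 4/16 = 0.250, OR 1.00.
- Stay 30% shorter (17.5): 4/13.5 = 0.296, OR 1.19.
- Common 81-day denominator, whatever the stay: (4/77)/(5/76) = 0.79.

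For control stays of 20 to 40 days and 3 to 6 event-days, the four in-hospital values range over 0.74–0.79, 0.85–0.88, 1.00 and 1.16–1.22.

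**2. Simulation under assumed rates.** There were 400,000 patients per arm, followed in daily steps for 81 days, all event-free at the start; 60% were lower-risk and 40% higher-risk. Control daily rates (lower/higher risk) were: onset 0.02/0.06, recovery 0.25/0.12, discharge while event-free 0.06/0.03, death during dysfunction 0.002/0.01. None of these comes from the documents. There are no events after discharge.

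| Assumed CoQ10 effect | Ever affected | Event-days | Hospital days | Patient OR | 81-day OR | In-hospital daily OR |
|---|---|---|---|---|---|---|
| Control | 41.8% | 5.21 | 25.0 | – | – | – |
| Onset −10% only | 39.6% | 4.77 | 24.7 | 0.91 | 0.91 | 0.91 |
| Onset −10%, discharge ×1.1, both types | 37.6% | 4.45 | 23.0 | 0.84 | 0.85 | 0.91 |
| Onset −10%, discharge ×1.25, both types | 35.2% | 4.09 | 20.8 | 0.76 | 0.77 | 0.93 |
| Onset −10%, discharge ×1.5, lower-risk only | 35.7% | 4.52 | 21.3 | 0.77 | 0.86 | 1.02 |
| No onset effect, discharge ×1.5, lower-risk only | 37.6% | 4.93 | 21.5 | 0.84 | 0.94 | 1.13 |

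Arithmetic for the fifth row (onset −10%, discharge ×1.5, lower-risk only):
- Patient: (0.357/0.643)/(0.418/0.582) = 0.77.
- Common window: (4.52/76.48)/(5.21/75.79) = 0.86.
- In hospital: 4.519/21.279 = 0.2124 (odds 0.2696), against 5.209/24.997 = 0.2084 (odds 0.2632); ratio 1.02.

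**3. Working correlation.** With an exchangeable structure, each patient's rows are weighted by 1/(1 + (n − 1)α), where n is the number of rows, so long-stayers count for less. With the fitted α of about 0.5, the fifth row gives about 0.90 instead of 1.02. The plan does not say which structure will be used.

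**4. The pilot.** Table 1 gives stays of 22.0 ± 3.4 and 21.9 ± 5.3 days, 15 per arm. Reading the ± values as standard errors, the standard error of the difference is √(3.4² + 5.3²) = 6.3 days. An approximate 95% interval is 0.1 ± 12.3 days, and a 20% difference is 0.20 × 21.9 = 4.4 days.

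**The case against.** **Row unit.** The plan never says that rows are days or weeks. If rows were the event types, each patient would supply a fixed number and the denominator would not depend on stay. This stands: direction and size cannot be fixed from the documents. It is also the first thing to correct, because an undefined row unit leaves the estimate undefined.

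**Other analyses exist.** A reader might infer that GEE is the main test of secondary endpoint 1. The documents do not say so: that endpoint is defined as binary events and their times, and chi-square and Cox analyses are also listed. The incidence of each event is nevertheless assigned to GEE by name, and nothing ranks the methods.

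**Missing-data cover.** A reader might infer that GEE has no protection at all. That is too strong, because multiple imputation is offered for all endpoints and systematic differences in missingness are to be taken into account. But the imputation is conditional, has no stated trigger or model, and does not count discharge as missing. One can also argue that days after discharge lie outside the endpoint window and are not missing at all. That is an estimand choice, and the plan does not make it.

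**Equal stay.** The pilot saw no difference in stay, and with equal stay nothing is lost. This stands as a condition. The pilot is too small to exclude a difference of 20%, and it enrolled burns from 5% TBSA upward, against 20% to 70% here.

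**The alternative also depends on stay.** A yes/no value benefits from shorter observation. With no effect on onset, the last row of the table gives a patient OR of 0.84. This is correct and has to be declared alongside the result.

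**Conclusion.** The point holds conditionally. If rows are hospital periods and CoQ10 shortens stay, the GEE odds ratio does not answer the per-patient question, and it can be diluted or reversed. In the illustration a patient-level OR of 0.77 (0.86 over a common 81 days) becomes 1.02. With onset cut alone, all three are about 0.91.

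A reader might infer that the planned GEE necessarily loses the benefit. The documents do not support this. The loss is nil with equal stay and partial with modest differences (0.84 against 0.91 when discharge is 1.1 times faster in both risk types). It is complete only when stay shrinks at least in proportion to event-days. The crossing of 1 also rests on an independence working correlation and, in the simulation, on faster discharge confined to lower-risk patients. All rates are assumed.

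Only a secondary analysis is affected. The primary composite is one count per patient and is not fitted by GEE. The change should be made before unblinding, because a null or reversed odds ratio could not otherwise be interpreted.

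**What to change.** For secondary endpoint 1, amend the Data Analysis section as follows.

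1. **Lead comparison.** Use one yes/no value per randomised patient for each event within the protocol window, with a risk difference and 95% CI. This matches the binary definition of the endpoint and the incidence rates in Table 6. State that the measure also reflects any effect on length of stay, and report it beside length of stay.
2. **Repeated events.** Compare the mean number of episodes per randomised patient to week 12, with death as a terminal event and robust standard errors. Count days after live discharge as event-free, and state this as an assumption, since nothing is collected after discharge. Define when a new episode begins.
3. **GEE.** Keep it as supportive only. State the row unit, the working correlation and the status of days after discharge and death. If rows are hospital periods, label the odds ratio accordingly or weight rows by the inverse probability of still being in hospital.
4. **Missing data.** Say whether discharge counts as missing, and what triggers multiple imputation and with which model.

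The cost is SAP wording; no new data are needed. The per-day odds ratio is no longer the headline estimate.
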